9.5.1.2 Alternate Primary Efficacy Analysis (Sliding Dichotomy)

If the proportional odds assumption cannot be justified, a sliding dichotomy of the GOS outcome at 6 months following injury, following categorization of subjects into different prognosis groups (worst, intermediate, and best) based on baseline prognostic factors, will be the primary efficacy analysis. The primary sliding dichotomy analysis will be based on imputation of missing data (covariates and 6-month GOS assessments).

For each subject a baseline prognostic risk score (BPRS) will be calculated as a weighted linear function of baseline prognostic factors of age, age squared, GCS motor score, Marshall CT classification, pupillary reactivity, presence of hypoxia, presence of hypotension, and presence of traumatic subarachnoid hemorrhage. The weighting of the BPRS factors will be based on the prognostic model developed in Hukkelhoven et al (2005). The BPRS will be sorted from lowest to highest, noting that higher BPRS represent a worse prognosis, and split into tertiles which will represent best, intermediate and worst prognosis.

For the cohort predicted to have the worst outcome, the outcome of severe disability or better is considered a “favorable outcome,” while for the cohort predicted to have the best outcome, only the outcome of good recovery is considered a “favorable outcome.” For the middle cohort there is no difference from the dichotomized model, so that the outcomes of moderate disability and good recovery are pooled to define “favorable outcome.”

The hypothesis that the proportion of favorable responses observed in each treatment group is the same will be tested using the Cochran-Mantel Haenszel (CMH) Chi-Square test, adjusted for region.

Null Hypothesis: $H_0: p_1 = p_2$
Alternative Hypothesis: $H_1: p_1 \neq p_2$

where p_1 = proportion of favorable responses in the BHR-100 treated group and p_2 = proportion of favorable responses in the placebo treated group. The Mantel-Haenszel estimate of the common odds ratio and corresponding 95% CI will also be presented.

If the p-value from the test of the null hypothesis of $p_1 = p_2$ is less than 0.0003 (at the interim) or 0.0098 (at the final analysis), it will be concluded that there is a statistically significantly difference in the proportion of favorable responses between the 2 treatment groups.

In addition to the formal inference testing discussed above, the difference in proportion of favorable outcomes and associated 2-sided 95% confidence interval between the BHR-100 and placebo treatment groups will be calculated.

In addition to the primary analysis that tests whether the overall proportion of favourable responses is the same in each treatment group, the CMH test results and odds ratios by baseline prognosis grouping (best, intermediate, worse) will also be presented. The Breslow-Day test will be computed to test whether the odds ratios are different across the prognostic groups. A significant test result will not affect the validity of the overall test of a difference between treatment groups, but will aid in the interpretation of the results.

The analyses above will be repeated for the straight observed case analysis (no imputation of 6-month GOS or covariates) in the mITT population, the observed case analysis in the PP population, and the analysis of imputed missing values in the mITT population for US subjects only.

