8.3.1 Alternate Primary Efficacy Analysis: Sliding Dichotomy Model

If the proportional odds assumption cannot be justified, an analysis will be conducted using a sliding dichotomy ([Maas et al., 2006](#); [Murray et al., 2005](#)) of the GOS outcome at 6 months following injury, following categorization of patients into different prognosis groups (worst,

intermediate, and best) based on baseline prognostic factors. The hypothesis that the proportion of favorable responses observed in each treatment group is the same will be tested both within the baseline prognosis grouping (best, intermediate and worst) and overall using the Cochran-Mantel Haenszel Chi-Square test, adjusted for region.

If the p-value from the test of the null hypothesis of no difference in the proportion of favorable responses observed in each treatment group is less than 0.0003 (at the interim) or 0.0098 (at the final analysis), it will be concluded that there is a statistically significantly difference in the proportion of favorable responses between the 2 treatment groups.

If this analysis is not required as an alternate analysis to the Proportional Odds Model analysis, it will still be performed as an additional sensitivity analysis.

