9.5.1.3 Sensitivity Analysis (Dichotomized Model)

The GOS at 6 months post injury will be dichotomized into Good Recovery, Moderate Disability versus Severe Disability, Vegetative Status/Dead. As a supportive analysis, the binary outcome will be analyzed using logistic regression analysis. The logistic regression model will be fitted including the effect of treatment, geographic region (North America, Europe, Asia, and South America), age, GCS motor score, pupil response, and CT classification.

If $Y = \text{response} = \text{GOS at 6 months following injury}$.

Model

$Y_1 = 0$ (not event), if $Y = \text{vegetative state or dead, severe disability}$
 $Y_1 = 1$ (event), if $Y = \text{moderate disability, good recovery}$

The dichotomous logistic regression model can be expressed as follows:

$$\ln(P/(1 - P)) = \alpha_0 + \beta_1 X_1 + \beta_2 X_2 + \beta_3 X_3 + \beta_4 X_4 + \beta_5 X_5 + \beta_6 X_6,$$

where

- \ln is the natural logarithm,
- P = Probability of an ‘event’ (moderate disability, good recovery) = Probability that $Y = 1$,
- $P/(1 - P)$ = odds of an ‘event’,
- X_1 = treatment group,
- β_1 = effect of treatment,
- X_2 = region,
- β_2 = effect of region,
- X_3 = age,
- β_3 = effect of age,
- X_4 = GCS motor score,
- β_4 = effect of GCS motor score,
- X_5 = pupil response,
- β_5 = effect of pupil response, and
- X_6 = CT classification,
- β_6 = effect of CT classification.

The logistic regression model will be used to test the null hypothesis that the odds of an ‘event’, i.e. observing a response of moderate disability or good recovery on the outcome variable, GOS at 6 months following injury, adjusted for region, age, GCS motor score, pupil response, and CT classification is the same in both treatment groups, i.e.

Null Hypothesis: $H_0: \beta_1 = 0$
Alternative Hypothesis: $H_1: \beta_1 \neq 0$

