	Favorable	n (%)	xx (xx.x %)	xx (xx.x %)		
	Unfavorable	n (%)	xx (xx.x %)	xx (xx.x %)		
Intermediate	n	n	xx	xx	0.xxxx	xx.x (xx.x, xx.x)
	Favorable	n (%)	xx (xx.x %)	xx (xx.x %)		
	Unfavorable	n (%)	xx (xx.x %)	xx (xx.x %)		
Worst	n	n	xx	xx	0.xxxx	xx.x (xx.x, xx.x)
	Favorable	n (%)	xx (xx.x %)	xx (xx.x %)		
	Unfavorable	n (%)	xx (xx.x %)	xx (xx.x %)		

Note: Missing values are first imputed by carrying forward the Month 3 GOS assessment. If a subject has neither the 3 nor the 6 month GOS, the missing value is imputed based upon the primary proportional odds model. Missing covariates are imputed as the most common level over all subjects. Percentages are based on the number of subjects in each treatment group in the population of interest.

¹ P-value is based on Cochran-Mantel Haenszel Chi-Square test adjusted for region.

² Difference is in proportion of favourable outcomes. The confidence interval for the difference is the standard Wald asymptotic confidence interval based on the normal approximation to the binomial distribution.

Source: Listing 16.2.6.2.

Program: xxxxxxx.sas, Output: xxxxxxx.rtf, Generated on: DDMONYYYY xx:xx, Page x of x

Table 14.2.2.4 Summary of Sliding Dichotomy (Dichotomization) at 6 Months Post Injury - Observed Values (mITT Population)

Table 14.2.2.5 Summary and Analysis of Sliding Dichotomy at 6 Months Post Injury - Observed Values (mITT Population)

Table 14.2.2.6 ORs¹ and 95% CIs² for Sliding Dichotomy at 6 Months Post Injury - Observed Values (mITT Population)

Table 14.2.2.7 Summary of Sliding Dichotomy (Dichotomization) at 6 Months Post Injury - Observed Values (PP Population)

Table 14.2.2.8 Summary and Analysis of Sliding Dichotomy at 6 Months Post Injury - Observed Values (PP Population)

Table 14.2.2.9 ORs¹ and 95% CIs² for Sliding Dichotomy at 6 Months Post Injury - Observed Values (PP Population)

Table 14.2.2.10 Summary of Sliding Dichotomy (Dichotomization) at 6 Months Post Injury for US Only - Missing Values Imputed (mITT Population)

Table 14.2.2.11 Summary and Analysis of Sliding Dichotomy at 6 Months Post Injury for US Only - Missing Values Imputed (mITT Population)

Table 14.2.2.12 ORs¹ and 95% CIs² for Sliding Dichotomy at 6 Months Post Injury for US Only - Missing Values Imputed (mITT Population)

Table 14.2.2.3 ORs¹ and 95% CIs² for Sliding Dichotomy at 6 Months Post Injury - Missing Values Imputed (mITT Population)

Characteristic	Prognosis	p-value	OR ³ (95% CI)

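### If proportional odds fails, the replacement primary test adjusts for region only; adding the prognostic score would gain about 1 to 2 points of power on the design's marginal odds ratio, and up to about 7 if the effect is conditional on prognosis

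*SAP*

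**What the plan says.** SAP 9.5.1.2 states the trigger: "If the proportional odds assumption cannot be justified, a sliding dichotomy of the GOS outcome at 6 months following injury" becomes the primary efficacy analysis, tested at 0.0003 at the interim and 0.0098 at the end. "For each subject a baseline prognostic risk score (BPRS) will be calculated as a weighted linear function of baseline prognostic factors"; the scores are then "split into tertiles which will represent best, intermediate and worst prognosis". The tertile decides what counts as favorable: severe disability or better in the worst group, moderate disability or better in the middle group, good recovery only in the best group.

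The overall hypothesis "will be tested using the Cochran-Mantel Haenszel (CMH) Chi-Square test, adjusted for region". Protocol 8.3.1 specifies testing "both within the baseline prognosis grouping (best, intermediate and worst) and overall using the Cochran-Mantel Haenszel Chi-Square test, adjusted for region", and keeps the analysis as a sensitivity analysis if it is not needed as the alternate. The footnote to shell Table 14.2.2.2 reads "P-value is based on Cochran-Mantel Haenszel Chi-Square test adjusted for region", and the odds-ratio footnote of Table 14.2.2.3 also names region only. By-tertile CMH results, odds ratios and a Breslow-Day test are reported in addition.

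The other models differ. The proportional odds model (POM, 9.5.1.1) and the Cox model (9.5.3.1) include region, age, GCS motor score, pupil response and CT class. So does the supportive fixed dichotomy in 9.5.1.3: "The logistic regression model will be fitted including the effect of treatment, geographic region", followed by the same four prognostic covariates.

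**The concern.** The analysis that can replace the POM as the deciding test uses less baseline information in its test statistic than the POM it replaces, and less than the supportive model beside it. No reason is given. Within each tertile, the chance of a favorable outcome still varies with prognosis, and a region-only test leaves that variation as noise. All the inputs are already collected.

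What is at stake is power. The trial was sized for 90% power under the adjusted POM's framework, and neither document states a power for the fallback.

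**Working it through.** **Inputs from the documents.** N = 1180 at 1:1, common odds ratio (OR) 1.5, placebo distribution 31/21/19/29% (good recovery, moderate disability, severe disability, vegetative/dead), two-sided 1% and 90% power (SAP 3.1); final threshold 0.0098 and the tertile cuts (SAP 9.5.1.2). Missing outcomes are imputed, so N is not reduced for dropout.

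**Assumed, because the documents do not give it.** The BPRS is a normally distributed score on the log-odds scale with SD 0.6 to 1.7. This corresponds to an AUC of 0.66 to 0.835 for good recovery or moderate disability versus worse. The score is taken as the true predictor, and region has no effect on outcome.

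**Step 1: reproduce the design.** Whitehead's formula is N = 12(z_α/2 + z_β)² / [(ln OR)²(1 − Σ q̄³)]. OR 1.5 turns the placebo distribution into 40.3/21.6/16.7/21.4%. The averaged categories are 35.6/21.3/17.8/25.2%, so 1 − Σ q̄³ = 0.9234. Then N = 12(2.576 + 1.282)² / (0.4055² × 0.9234) ≈ 1176, against the planned 1180. Power at 1180 is 90.1% at 0.01 and 90.0% at 0.0098, against 90% stated (90.66% in Table 3). The design reproduces.

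**Step 2: power of the sliding dichotomy.** Cut-points were calibrated so that the placebo marginals are 31/21/19/29, and the SAP's favorable cuts were applied by tertile.
- CMH: z = Σ(n₁n₀/n)(p₁ − p₀) / √Σ[n₁n₀ p̄(1 − p̄)/(n − 1)], summed over strata.
- Adjusted logistic regression: z = β_treatment / SE.
- Power = Φ(z − 2.583).

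Power (%) at N = 1180, two-sided 0.0098. Each cell gives region only / plus tertile strata / logistic with tertile and continuous score. Gains compare the last with the first and come from unrounded values.

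| AUC | OR 1.5 marginal | Gain | OR 1.5 conditional | Gain |
|---|---|---|---|---|
| 0.658 | 84.3 / 84.8 / 85.3 | 1.0 | 77.7 / 78.2 / 78.9 | 1.2 |
| 0.721 | 89.4 / 89.4 / 90.5 | 1.1 | 76.8 / 76.8 / 78.4 | 1.6 |
| 0.772 | 93.0 / 93.1 / 94.4 | 1.5 | 73.9 / 74.3 / 77.0 | 3.1 |
| 0.813 | 95.4 / 95.9 / 97.1 | 1.7 | 69.9 / 71.1 / 75.1 | 5.2 |
| 0.835 | 96.6 / 97.1 / 98.2 | 1.6 | 66.8 / 68.8 / 73.6 | 6.8 |

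**Step 3: non-proportional effects, the setting in which this test would be primary.** With odds ratios 1.7/1.5/1.3 or 1.3/1.5/1.7 across the three cuts, the gain is 0.8 to 2.2 points (marginal) and 1.0 to 7.3 (conditional) over the same AUC range.

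**Step 4: where the gain comes from.** The sliding cut already brings the tertiles' favorable rates close together: on placebo 0.51/0.52/0.52 (best/middle/worst) at AUC 0.72, and 0.63/0.53/0.40 at AUC 0.835. Tertile strata alone therefore add only 0 to 2.0 points (2.5 at most with non-proportional effects). The rest comes from the continuous score within tertiles. In a separate simulation with assumed covariates, adjusting only for the four POM covariates gained about 1 to 3 points.

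**Step 5: the 5% tier in SAP 9.5.1.4.** Converting by normal approximation and ignoring the small interim adjustment, at AUC 0.835 (conditional):
- Region only: z = 2.583 + Φ⁻¹(0.668) = 3.017; power = Φ(3.017 − 1.960) = 85.5%.
- With score: z = 2.583 + Φ⁻¹(0.736) = 3.214; power = Φ(3.214 − 1.960) = 89.5%.

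The gain is 4.0 points. At AUC 0.658 it is 91.7% to 92.3%, or 0.6. The least favorable non-proportional case in this AUC range (63.3% to 70.6% at 0.0098) becomes 83.2% to 87.8%, or 4.6. On the marginal reading, with proportional effects, the gain at this tier is at most about half a point.

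**Step 6: validity.** In null simulations the Type I error was 0.009 to 0.011 for all the tests compared.

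**The case against.** The strongest reply is that the specified test is sound. It tests the stated null, equality of two marginal proportions, stratified by the randomization factor, and a risk difference is reported beside it. That stands: this is about efficiency only.

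It also stands that OR 1.5 is applied to the marginal GOS distribution in the sample-size calculation. On that reading the gain is only 1 to 2 points, and the region-only test already has about 89% power or more once the AUC reaches about 0.72. The larger figures need OR 1.5 to be conditional on prognosis.

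A further argument is that one BPRS slope across three different GOS cuts brings back a proportionality constraint just after proportionality was rejected. It does not change the result: letting the slope differ by tertile gave the same power. The adjusted logistic models planned at each fixed cut (9.5.1.1 and 9.5.1.3) are useful support, but they do not replace the deciding test.

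A reader might infer more than the documents support:
- That the prognostic score is thrown away. It is not: it sets the tertile and favorable cut for every subject and structures the by-tertile reporting.
- That the fallback stands or falls at 0.0098 alone. Section 9.5.1.4 adds a 5% tier, where the loss is smaller.
- That this is the least adjusted 6-month GOS analysis. An unadjusted POM is also planned (Tables 14.2.1.13 and 14.2.1.14).

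**Conclusion.** The point holds as a cheap improvement. The overall sliding-dichotomy test adjusts for region alone and gives up some power that baseline data already in hand could recover.

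At two-sided 0.0098 and N = 1180 the loss is about 1 to 2 points if OR 1.5 is marginal and about 1 to 7 points if it is conditional on prognosis. At the 5% tier, the conditional range shrinks to about 1 to 4 or 5 points.

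These sizes rest on an assumed BPRS AUC of about 0.66 to 0.84, which the documents neither confirm nor exclude, and on a score that captures prognosis fully, so they are best cases. Seven points should not be read as the expected loss. Nothing here makes the region-only test invalid.

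**What to change.** Before unblinding, specify the overall sliding-dichotomy test in SAP 9.5.1.2 as a logistic regression of favorable outcome on treatment, region, prognosis group and continuous BPRS, with treatment tested at the same 0.0003 and 0.0098. The four POM covariates in place of the BPRS are an acceptable alternative, with a gain of about 1 to 3 points. Adding tertile strata to the CMH test alone would achieve little. Keep the region-stratified CMH result and the risk difference as supporting rows. Update Protocol 8.3.1 and Tables 14.2.2.2 and 14.2.2.3 to match. Consider the same change for the GOS-E sliding dichotomy in 9.5.2.3, which was not simulated.

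No new data are needed. The BPRS is already derived, SAP Section 5 gives imputation rules for its components other than age, and date of birth is entered at screening (Protocol 6.2). The model is one further PROC LOGISTIC fit.

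There are two costs. The reported odds ratio becomes conditional on prognosis, as it already is in the POM. And SAP 1.1 shows that the change of analysis population went through the Special Protocol Assessment, so replacing the alternate primary test may need agreement there too.

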9.5.1.3 Sensitivity Analysis (Dichotomized Model)

The GOS at 6 months post injury will be dichotomized into Good Recovery, Moderate Disability versus Severe Disability, Vegetative Status/Dead. As a supportive analysis, the binary outcome will be analyzed using logistic regression analysis. The logistic regression model will be fitted including the effect of treatment, geographic region (North America, Europe, Asia, and South America), age, GCS motor score, pupil response, and CT classification.

If $Y = \text{response} = \text{GOS at 6 months following injury}$.

Model

$Y_1 = 0$ (not event), if $Y = \text{vegetative state or dead, severe disability}$
 $Y_1 = 1$ (event), if $Y = \text{moderate disability, good recovery}$

The dichotomous logistic regression model can be expressed as follows:

$$\ln(P/(1 - P)) = \alpha_0 + \beta_1 X_1 + \beta_2 X_2 + \beta_3 X_3 + \beta_4 X_4 + \beta_5 X_5 + \beta_6 X_6,$$

where

- \ln is the natural logarithm,
- P = Probability of an ‘event’ (moderate disability, good recovery) = Probability that $Y = 1$,
- $P/(1 - P)$ = odds of an ‘event’,
- X_1 = treatment group,
- β_1 = effect of treatment,
- X_2 = region,
- β_2 = effect of region,
- X_3 = age,
- β_3 = effect of age,
- X_4 = GCS motor score,
- β_4 = effect of GCS motor score,
- X_5 = pupil response,
- β_5 = effect of pupil response, and
- X_6 = CT classification,
- β_6 = effect of CT classification.

The logistic regression model will be used to test the null hypothesis that the odds of an ‘event’, i.e. observing a response of moderate disability or good recovery on the outcome variable, GOS at 6 months following injury, adjusted for region, age, GCS motor score, pupil response, and CT classification is the same in both treatment groups, i.e.

Null Hypothesis: $H_0: \beta_1 = 0$
Alternative Hypothesis: $H_1: \beta_1 \neq 0$

If the p-value from the test of the null hypothesis of $\beta_1 = 0$ is less than 0.05, it will be concluded that BHR-100 is statistically significantly different from placebo with respect to the GOS at 6 months following injury. The odds of an 'event' (moderate disability or good recovery) in the GOS at 6 months will be modeled and the corresponding common odds ratio for treatment, e^{β_1} , can then be interpreted to determine the direction of the treatment difference as follows. With the placebo group being considered as the reference category, if the odds ratio ($OR_{BHR-100/placebo}$) is greater than 1, the odds of a favorable outcome in the GOS at 6 months is greater in the BHR-100 treatment group compared to placebo.

The logistic regression analysis will be fitted in SAS[®] using the PROC LOGISTIC procedure.

Goodness of fit of the model will be assessed as outlined above for the Proportional Odds Model.

The individual p-values associated with the tests of effects (treatment, geographic region, age, GCS motor score, pupil response, and CT classification) will be summarized for the Logistic Regression Model of GOS at 6 months post injury.

The odds ratios and associated 95% CIs for the levels of effects relative to a reference category will be presented for all factors and covariates included in the Logistic Regression Model of GOS at 6 months post injury.

In addition to the results of the hypothesis tests from the statistical modeling, the number of non-missing observations, absolute and relative frequency (n and percentages), will be provided by treatment group for the dichotomized GOS categories at 6 months post injury.

The primary dichotomized analysis will be based on missing values of 6-month GOS and covariates imputed. It will also be repeated for the straight observed case analysis (no imputation of 6-month GOS or covariates) in the mITT population and the straight observed case analysis in the PP population.

A bar chart illustrating the percentage of responses in each of the dichotomized categories for each treatment group will be produced for the GOS at 6 months (observed values and missing values imputed) for the mITT population.

